#### Part B:

Visit 4-6 – During these visits' participants will perform 6xDC at various gradients of between 3-8% at a speed of 1.5km/h as above. These will be performed in a randomised order. During each test ECG, Q (PhysioFlow, Manatec Biomedical, Paris, France), HR and SpO2 (RAD-5v Masimo Corp, Irvine, CA, USA) will be monitored continuously throughout the test. Ratings of ED will be participant self-reported every 10 seconds using a 0-10 Numerical Rating Scale (NRS) on a PC-based system with a computer monitor mounted in-front of the treadmill. At the end of each test, as per previous tests, the MDP will be completed to assess the sensory and affective components of ED.

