Considering the above limitations Morris et al. [25] recently developed a two-minute treadmill dyspnea challenge in which participants walk at a given speed at an individualised gradient. The aim was to evaluate its repeatability and sensitivity using a high (mean rate: mean gradient of  $4.0\pm0.6$ km/h:  $10\pm2\%$ ) and a low (rate: mean gradient of  $4.0\pm0.6$ km/h:  $6\pm2\%$ ) intensity challenge. The speed was set at 80% of the 6MWT speed and ED was measured continuously using a digital 0-10 scale. They concluded that the dyspnea challenge test is safe, repeatable and sensitive to change in ED. A small sample size is the biggest limitation of this work so far and further study is needed to confirm these findings. The aim of the current research is to continue the development of the dyspnea challenge within COPD patients not only to test its ability to measure ED in a patient population but also to assess the sensitivity of the protocol to changing intensities of exercise. Furthermore, the dyspnea challenge will undergo pre and post intervention testing, both for an acute and longer term interventions, to assess its validity.

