# • Study Objectives

#### Aims

The overarching aim of the current study is to develop a 2-minute walk treadmill test to evaluate dyspnea. The primary aims are to assess:

- i. the relationship between 6MWD and exertional dyspnea scores within a 6MWT when compared against exertional dyspnea scores recorded during the dyspnea challenge.
- ii. the sensitivity of the dyspnea challenge to changes in exertional dyspnea via changes to the gradient of the treadmill.
- iii. Compare the exertional dyspnea response to the dyspnea challenge in heart failure, pulmonary hypertension and COPD.
- iv. To assess the responsiveness of the dyspnea challenge to changes in exertional dyspnea experienced post an acute intervention and exercise rehabilitation programs (Pulmonary and Heart Failure rehabilitation programs).

Secondary aims, of the study, will be:

- v. To compare the metabolic cost of the 6MWT and the dyspnea challenge.
- vi. To compare the metabolic cost of the dyspnea challenge between cardiopulmonary disease populations.
- vii. Establish a minimally important difference (MID) for the dyspnea challenge.

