## d. Study Procedure

Participants may be required to complete all three parts of this study, there are a total of nine visits over the three parts. Visits 1-3 will address question one and investigate the ability of the 6MWT and its outcome measure of six-minute walk distance (6MWD) to act as a surrogate measure of exertional dyspnea (ED). The secondary outcomes are to non-invasively monitor cardiopulmonary factors to compare the metabolic costs of both tests and compare this across disease population. Visits 4-6 will address question two and consider the sensitivity of the dyspnea challenge in heart and lung disease groups by asking individuals to perform the dyspnea challenge at differing gradients ranging from 3 to 8%. Visits 7-9 will address question four and secondary aim seven to assess the responsiveness of the dyspnea challenge in heart and lung disease groups by asking individuals to perform the dyspnea challenge pre and post an intervention that has proven to increase or decrease dyspnea. There will be an acute challenge using a chest wall binder that will be applied only to COPD participants which is known to increase dyspnea and then a longer term intervention being that of Pulmonary and Heart Failure Rehabilitation which is known to improve dyspnea in the COPD and HF populations. Participants will complete two dyspnea challenges pre and post the exercise rehabilitation programs which will be completed outside of this study. Participants included in the acute challenge part of the study will complete the dyspnea challenge in random order on two separate visits with and without a chest wall binder fitted.

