The DC will be performed be on a treadmill in a temperature-controlled laboratory. Participants will walk on a treadmill for 2-minutes at a speed of 3km/h and a gradient of 4%. Perrault *et al.*, [17] found that 93% of patients suffering from moderate-severe COPD managed to complete a 3-minute walk test at 1.5km/h on a flat surface and that only 84% managed to complete the test at 2.5km/h. The gradient selected was chosen as previous research in 8 participants with mild COPD managed to achieve a 2-minute challenge at between 4-6% gradient[25]. Electrocardiogram (ECG), Heart rate (HR) and oxygen saturation (SpO2) will be monitored continuously using a portable saturation monitor (RAD-5v Masimo Corp, Irvine, CA, USA). Ratings of ED will be participant self-reported every 10 seconds using a 0-10 Numerical Rating Scale (NRS) on a PC-based system with a computer monitor mounted in front of the treadmill. Pulmonary gas exchange (Metamax, Cortex BXB, Lepzig, Germany), cardiac output (Q) (PhysioFlow, Manatec Biomedical, Paris, France) and muscle tissue oxygen saturation (MtO2) (PortaMon Artinis Medical Systems, Einsteinweg, The Netherlands) will be monitored continuously. At the end of the test, sensory and affective measures of ED will be assessed using the MDP[30].

Visit 2 and 3 – During these two visits, participants will perform 2x6MWT and 2xDC. These tests will be performed in a randomised order with 30 minutes of rest in between. 1x6MWT and 1xDC will be performed as above with the same equipment and measures assessed. The other two tests they will be performed without the pulmonary gas exchange measures being assessed. This is to negate the impact of the face mask on self-perceived ratings of exertional dyspnea. During these two tests, ECG, Q, MtO2, HR, SpO2, and blood pressure will be monitored as above. At the end of each test the MDP will be performed.

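### The dyspnea challenge has two unreconciled speeds, 3 km/h in Part A and 1.5 km/h in Part B, and no stated setting in Part C

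*Protocol*

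**What the plan says.** Four places in the protocol bear on the treadmill setting.

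- **Study Procedure, Part A**, defines the test: "Participants will walk on a treadmill for 2-minutes at a speed of 3km/h", at a gradient of 4%. (The unit is printed with a stray exponent and is read here as km/h.) The supporting text cites a study in which most patients "managed to complete a 3-minute walk test at 1.5km/h on a flat surface and that only 84% managed to complete the test at 2.5km/h". That is a different test.
- **Study Procedure, Part B**, runs the same named test six times in random order: "participants will perform 6xDC at various gradients of between 3-8% at a speed of 1.5km/h as above".
- **The overview that opens the Study Procedure** describes Part B only by its slopes. Participants are to "perform the dyspnea challenge at differing gradients ranging from 3 to 8" per cent, and no change of speed is mentioned.
- **Study Procedure, Part C**, has two dyspnea challenges at each of visits 7, 8 and 9 and gives neither speed nor gradient.

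Part B serves primary aim ii, which is to assess "the sensitivity of the dyspnea challenge to changes in exertional dyspnea via changes to the gradient of the treadmill".

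**The concern.** The back-reference in Part B sends the reader to a speed that is not there. The only dyspnea challenge described above it runs at 3 km/h, and the only earlier 1.5 km/h belongs to the cited flat walk. The protocol does not say that the speed is lowered on purpose, or why.

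Three things are at stake.

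1. **Meaning of the Part B result.** Primary aim i compares the dyspnea challenge with the six-minute walk test at the Part A setting. Primary aim ii asks how the dyspnea challenge responds to gradient. If the speeds differ by a factor of two, the sensitivity found in Part B belongs to another version of the test than the one examined in Part A.
2. **Conduct.** Data are collected at The Prince Charles Hospital, Griffith University, Bundaberg Health Promotions and Central Queensland University. Staff who read Part A closely and staff who read Part B closely could set different speeds in good faith.
3. **Part C.** The comparison before and after rehabilitation (primary aim iv) and the minimally important difference (aim vii) depend on a repeatable setting. With two speeds above it and none of its own, Part C has no unambiguous default.

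**Working it through.** The protocol states no climb rate or workload for these tests, so there is no figure of its own to reproduce. The check takes the settings as printed and computes the vertical climb rate.

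**Inputs.** Part A: 3 km/h, 4%, 2 minutes. Part B: 1.5 km/h, 3% to 8%, six tests. Whole-percent steps are assumed, since six tests fit 3, 4, 5, 6, 7 and 8%. The upper limit below does not depend on that assumption.

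**Formula.** Climb rate = belt speed × gradient.

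**Part A.** 3000 m/h × 0.04 = 120 m/h.

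**Part B, if 1.5 km/h is applied.**

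| Gradient | Climb rate | Ratio to Part A |
|---|---|---|
| 3% | 1500 × 0.03 = 45 m/h | 0.375 |
| 4% | 1500 × 0.04 = 60 m/h | 0.500 |
| 5% | 1500 × 0.05 = 75 m/h | 0.625 |
| 6% | 1500 × 0.06 = 90 m/h | 0.750 |
| 7% | 1500 × 0.07 = 105 m/h | 0.875 |
| 8% | 1500 × 0.08 = 120 m/h | 1.000 |

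The gradient needed at 1.5 km/h to match Part A is 3 × 4% / 1.5 = 8%, the top of the stated range. So no Part B test climbs faster than Part A, and only the steepest equals it.

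**Check on the definition of gradient.** If climb is taken as belt distance × sin(arctan(gradient)), 8% at 1.5 km/h gives 1.994 m/min and Part A gives 1.998 m/min. The conclusion is unchanged.

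**Distance.** In two minutes the belt travels 3000 × 2/60 = 100 m at the Part A speed and 1500 × 2/60 = 50 m at the Part B speed. A 4% test in Part B therefore has half the distance and half the climb of the Part A test at the same gradient, and is not a repeat of it.

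**For scale only.** At any one speed common to both parts, the ratios would be 3/4 = 0.75 to 8/4 = 2.0, against 0.375 to 1.0 as written. The Part A condition would then lie inside the Part B range instead of at its upper edge. This shows what the discrepancy does; it does not show which speed is intended.

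**The case against.** The best defence is that the back-reference may attach to the test procedure and equipment, not to the speed, and that a lower speed may have been chosen deliberately for slopes up to 8% in patients across GOLD I-IV, NYHA I-III and WHO I-III. This is possible. It would explain the wording, but the protocol would still run one named test at two speeds without saying so or giving a reason.

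Several stronger conclusions are tempting, and the documents do not support them.

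- **That speed is mixed up with gradient, so primary aim ii fails.** All six Part B tests share one stated speed, differ in gradient and are taken in random order. If that speed is used throughout, the contrast within Part B is internally valid. The Data Analysis section specifies no pooling or comparison of Part A with Part B scores, so no planned analysis is shown to break. The loss is one of interpretation.
- **That the Part B range is too low or too narrow to show a gradient effect.** The protocol gives no relation between climb rate and dyspnea, no variance and no target difference. Climb rate also leaves out the cost of level walking.
- **That the earlier dyspnea challenge study is a benchmark for the range.** The Background reports two mean settings, with individualised gradients, from that study. They do not define a span that Part B ought to cover.
- **That the Background adds a third conflicting rule.** The statement "The speed was set at 80% of the 6MWT speed and ED was measured continuously using a digital 0-10 scale" describes that earlier study. It is not an instruction in this protocol.
- **That Part C is contradictory.** It is silent. Inheriting the Part A definition is a natural reading, but with Part B in between it is not the only one.

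What stands is the unexplained difference in speed, its effect on how Part B relates to Part A, and the room it leaves for inconsistent conduct.

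**Conclusion.** The inconsistency is real and must be resolved. It concerns a core setting of the test under development, and nothing in the protocol reconciles the two speeds. Its size is a factor of two in belt speed. If 1.5 km/h is applied as printed, Part B covers 45 to 120 m/h against 120 m/h in Part A. If 1.5 km/h is a drafting slip, the climb comparison falls away and only the wrong text remains. The climb figures are therefore conditional, while the contradiction is not.

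The consequence is limited. The Part B gradient comparison remains valid at whatever single speed is used, but its conclusion carries over to the Part A test only by assumption. The risk that sites run different speeds, and that Part C is run at a setting nobody fixed, follows from the text as it stands. Whether either has happened cannot be told from the protocol.

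**What to change.** Reconcile Parts A and B of the Study Procedure before further testing, in one of two ways:

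- correct whichever speed is inconsistent with the intended design; or
- state that the difference is deliberate, give the reason, and limit the Part B conclusion to the speed at which it was obtained.

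In Part C, state which setting applies and keep it the same before and after rehabilitation. The choice of speed and gradient belongs to the investigators, and this review proposes none.

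For tests already done, record the speed actually used in each. If both speeds occur, account for speed in the analysis of the dyspnea scores.

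The cost is a short protocol clarification, a notice to the sites and, where testing has begun, a check of the test records. A mix of speeds that was never recorded could not be put right after data collection.

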#### Part C:

Visit 7 and 8 (COPD Participants Only) – Will be completed prior to commencing Pulmonary or Heart Failure Rehabilitation programs (chronic intervention, Figure 1) and the wearing of chest wall binders will only be completed by COPD participants (acute intervention, Figure 1). During these visits participants will be asked to complete 2x DCs per visit. Each test will be completed wearing a forehead oximeter to measure heart rate, rhythm and arterial oxygen saturation. Two of the four DC tests participants will wear a chest wall binder. These four tests will be performed in a random order. At the end of each test participants will be asked to complete the MDP.

Visit 9 – Will be completed after the completion of Pulmonary or Heart Failure Rehabilitation programs by participants. During this visit participants will be asked to complete 2xDC. Each test will be completed wearing a forehead oximeter to measure heart rate, rhythm and arterial oxygen saturation. At the end of each test participants will be asked to complete the MDP and TDI questionnaires.

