#### e. Outcome Measures

## 1. Primary outcome measure:

- a. Dyspnea (ED) -
  - Modified Borg 0-10 Scale A common measure taken during field-based testing. This will be measured using a 0-10 scale and does not involve any invasive procedures. This 0-10 scale has been used previously within COPD patients during the dyspnea challenge[25].
  - Multidimensional Dyspnea Profile (MDP): The MDP contains 11 items which participants rate on a continuous scale (0-10) and a forced-choice question for five sensory qualities [31]. The profile is split into three subsections; Sensory Dimension (SQ), Breathing Discomfort (A1) and Emotional Response (A2)[30]. This has been previously validated within clinical settings[32].
  - *Dyspnea*-12: A 12 descriptor item questionnaire that provides an overall score for breathlessness severity that matches the participants breathing 'these days'. It incorporates seven physical items and five affective items. Frequently used at baseline and during follow-up assessments[33].
  - Baseline and Transition Dyspnoea Index (BDI/TDI): The BDI/TDI measures the severity of breathlessness at the beginning of an intervention (BDI) then again at the end of the intervention (TDI). The questionnaire is comprised of three subsections; Functional Impairment, Magnitude of Task and Magnitude of Effort. This has been previously validated within clinical settings[34].

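### Part C labels its only pre-rehabilitation visits COPD-only, against aim iv and its own text, and no visit schedules the BDI that should precede the Visit 9 TDI

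*Protocol*

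**What the plan says.** **Who is tested before rehabilitation.** Primary aim iv (Study Objectives) is to assess responsiveness to an acute intervention and to both pulmonary and heart failure rehabilitation. The overview in Methods, d. Study Procedure, describes the longer-term intervention as "Pulmonary and Heart Failure Rehabilitation which is known to improve dyspnea in the COPD and HF populations" and sets the testing rule: "Participants will complete two dyspnea challenges pre and post the exercise rehabilitation programs which will be completed outside of this study". It limits only the binder challenge to COPD.

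Part C opens with "Visit 7 and 8 (COPD Participants Only". The same sentence continues "Will be completed prior to commencing Pulmonary or Heart Failure Rehabilitation programs (chronic intervention, Figure 1" and then says that "the wearing of chest wall binders will only be completed by COPD participants". On the number of tests: "During these visits participants will be asked to complete 2x DCs per visit". Two of these four are done with the binder. Visit 9, after rehabilitation, has two challenges and no disease restriction.

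**BDI and TDI.** Outcome Measures, section 1, places BDI/TDI under the primary outcome: "The BDI/TDI measures the severity of breathlessness at the beginning of an intervention (BDI) then again at the end of the intervention (TDI". For Visit 9, Part C says "At the end of each test participants will be asked to complete the MDP and TDI questionnaires". The questionnaires named for Visit 1 are the SGRQ or KCCQ, the mMRC, the Dyspnoea-12 and the HADS. Visits 2 to 8 name only the MDP.

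**The concern.** Part C is the only part of the study that serves aim iv. The Data Analysis section treats participants as their own controls, with time as a within-subject factor, so a group with no test before rehabilitation contributes nothing to the rehabilitation question. Sites are likely to work from the visit headings. A site that does so would invite heart failure participants to Visit 9 only.

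The second gap affects every participant in the rehabilitation part. The TDI records change from the state that the BDI captured. If no BDI is taken before the program starts, the TDI has no documented starting point, and one listed primary-outcome instrument cannot be used as the protocol defines it. Both gaps are permanent once a participant begins rehabilitation.

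**Working it through.** The protocol gives no figure to reproduce here. The check compares the visit schedule with the aims and outcome definitions, and counts tests.

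**1. Pre-rehabilitation challenges, by source**

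| Place in protocol | Heart failure tested before rehabilitation? |
|---|---|
| Aim iv, Study Objectives | Implied: responsiveness to heart failure rehabilitation needs a before and an after |
| d. Study Procedure, overview | Yes: two challenges before and two after; only the binder is limited to COPD |
| Part C, Visits 7 and 8, heading | No: COPD only |
| Part C, Visits 7 and 8, text after the heading | Yes by implication: timed before pulmonary or heart failure rehabilitation; COPD limit attached to the binder |
| Part C, Visit 9 | After rehabilitation only; no disease limit |

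**2. Count of Part C challenges**

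- COPD, before: 2 visits × 2 tests = 4. With the binder: 2. Without: 4 − 2 = 2. After: 2. The two unbound tests before and two after match the overview.
- Heart failure, following the heading: 0 before and 2 after, so 0 of 30 have a Part C pre/post pair. They would attend 9 − 2 = 7 of the nine visits.
- Heart failure, following the overview: 2 before and 2 after.

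The overview reading still leaves something open. Visits 7 and 8 are written as one procedure of four tests, two with the binder, in random order. With the binder removed, Part C does not say whether heart failure participants attend one visit or two. At two tests per visit, that means two or four challenges, and only two agrees with the overview.

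**3. Could Parts A and B serve as the baseline?** Heart failure participants do challenges with the MDP in both parts. Neither part is tied to a time before rehabilitation, and the two state different treadmill speeds (3 km/h in Part A, 1.5 km/h in Part B). They do not supply a matched pre-rehabilitation test.

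**4. BDI and TDI**

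- Visits that name the BDI: 0 of 9.
- TDI administrations at Visit 9 as written: 2 tests × 1 each = 2. The outcome definition calls for one rating, at the end of the intervention.

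**5. Eligibility.** Section c. Study Population lists having completed a pulmonary or cardiac rehabilitation program at one of the recruiting services among the criteria to be met. Visits 7 and 8 are to take place before rehabilitation starts. The two do not fit together, for COPD or for heart failure.

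**The case against.** The best defence is that the heading is a drafting slip. The words that follow it cover heart failure rehabilitation and attach the COPD restriction to the binder, and the overview says the same. Figure 1, cited twice in that sentence, is not reproduced in the text available and may show who attends. This stands in part: the exclusion of heart failure is one of two readings, not an established fact. It does not remove the problem, because the heading is the operative instruction for the visit and no text says which visit a heart failure participant attends.

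On the BDI, the outcome section does commit to measuring it at the start of an intervention. That is correct. What is missing is its allocation to a visit, so the statement that no BDI will be collected would go too far.

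A reader might draw four stronger conclusions that the protocol does not support:

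- **That the pre/post confidence interval widens by √(60/30) = 1.41.** This needs all 60 COPD and heart failure participants to enter Part C, one pooled change estimate and equal standard deviations. The protocol says only that participants may be required to complete all parts, and it never says the diseases are pooled. Analysed separately, the COPD interval is unaffected.
- **That the minimally important difference (aim vii) has nothing to be scored against.** The protocol names no anchor. COPD has two unbound challenges with the MDP on each side of rehabilitation, so an MDP-based or distribution-based estimate remains possible.
- **That the Dyspnea-12 must be repeated.** It appears under the primary outcome and is scheduled only at Visit 1, but no text promises a change score for it.
- **That heart failure contributes Visit 9 only.** Parts A and B also include heart failure; the gap concerns Part C.

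**Conclusion.** The point holds as two defects in the Part C schedule.

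First, the heading of Visits 7 and 8 contradicts aim iv, the Study Procedure overview and the rest of its own sentence. If the heading is followed, 0 of the planned 30 heart failure participants have a Part C challenge before rehabilitation, and responsiveness to heart failure rehabilitation cannot be estimated. If the overview is followed, the gap closes, apart from the unstated visit and number of tests. The size therefore depends on which text sites use.

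Second, whichever reading applies, the BDI has no scheduled visit, so the TDI has no recorded baseline in any disease group; the TDI is also set twice in one visit. This rests on the visit descriptions as written.

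This is more than missing detail, because a primary aim and a listed primary-outcome instrument both depend on data that cannot be collected after rehabilitation begins. It should be corrected before Part C runs.

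**What to change.** 1. Reconcile the Part C heading with the overview: the unbound pre-rehabilitation challenges apply to COPD and heart failure, and only the binder tests are COPD-only. State which visit heart failure participants attend and that they complete two unbound challenges there, as the overview has it.
2. Schedule the BDI at the pre-rehabilitation visit for every participant in the rehabilitation part.
3. Give the TDI once at Visit 9. The MDP can stay after each test.
4. Reconcile the pre-rehabilitation visits with the criterion in section c. Study Population that participants have completed a rehabilitation program. Without this, the first change does not secure a pre/post sample in either disease.

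Using the TDI as an anchor for the minimally important difference is an option for the investigators, not a correction.

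The cost is an amendment to the wording, one short questionnaire, and a heart failure visit that aim iv already assumes. Dropping the second TDI saves a little time.

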#### **Exclusion Criteria:**

- Musculoskeletal disorders that prevent walking on the treadmill.
- Significant co-morbidities that would exclude exertional exercise or any contraindications to exercise as defined by the American College of Sports Medicine.
- Oxygen therapy that would exclude the wearing of portable metabolic cart.
- Chest wall binder Part C of study only Extensive cardiac history and/or untreated high blood pressure.

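### The COPD-only label on Visits 7 and 8 contradicts the protocol's own rehabilitation plan; if sites follow it, heart failure participants have no designated pre-rehabilitation challenge for primary aim iv

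*Protocol*

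**What the plan says.** Primary aim iv (Protocol, Aims) is "To assess the responsiveness of the dyspnea challenge to changes in exertional dyspnea experienced post an acute intervention and exercise rehabilitation programs", and its parenthesis names the pulmonary and the heart failure programmes.

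The overview in d. Study Procedure splits this into two experiments. The chest wall binder is the acute one, for COPD only. The other is a "longer term intervention being that of Pulmonary and Heart Failure Rehabilitation which is known to improve dyspnea in the COPD and HF populations". For the latter it says: "Participants will complete two dyspnea challenges pre and post the exercise rehabilitation programs".

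The visit schedule in Part C begins: "Visit 7 and 8 (COPD Participants Only) – Will be completed prior to commencing Pulmonary or Heart Failure Rehabilitation programs". The sentence continues that "the wearing of chest wall binders will only be completed by COPD participants (acute intervention, Figure 1"). On content it says "During these visits participants will be asked to complete 2x DCs per visit" and "Two of the four DC tests participants will wear a chest wall binder". Visit 9 follows completion of either programme, contains two challenges and carries no disease restriction.

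The Exclusion Criteria contain one item tied to the binder: "Chest wall binder Part C of study only Extensive cardiac history and/or untreated high blood pressure".

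**The concern.** Responsiveness to rehabilitation is a within-person change, so each participant needs a challenge before the programme and one after it. Visits 7 and 8 are the only visits placed before rehabilitation, and their label admits COPD participants only. A site working from the Part C schedule could reasonably bring heart failure participants in for Visit 9 alone.

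Heart failure would then have post-rehabilitation scores with nothing designated to subtract from them. That part of a primary aim would have no planned estimate, and aim vii would receive no rehabilitation change from heart failure. The loss is permanent for each participant once the programme has begun.

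Reading the label loosely does not settle the matter either. If heart failure participants do attend, the only test list is four challenges, two of them with a binder that the protocol withholds from them. It does not say whether they do two or four challenges, or at one visit or two.

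**Working it through.** The protocol states no figure to reproduce on this point. The check is a count of scheduled challenges and a comparison of the texts.

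**Inputs.** Planned numbers are 30 COPD, 30 heart failure and 30 pulmonary hypertension (c. Study Population). Challenges per visit come from Parts A, B and C of d. Study Procedure.

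**Visits 7 and 8.** 2 challenges × 2 visits = 4, which agrees with the four tests named in Part C. With 2 bound, 4 − 2 = 2 are unbound. These 2 match the two pre-rehabilitation challenges in the overview and the 2 at Visit 9.

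**Challenges per participant:**

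| Visits | Settings stated | COPD | Heart failure, label followed | Heart failure, overview followed |
|---|---|---|---|---|
| 1 | 3 km/h, 4% | 1 | 1 | 1 |
| 2–3 | as Visit 1 | 2 | 2 | 2 |
| 4–6 | 1.5 km/h, 3–8% | 6 | 6 | 6 |
| Before rehabilitation (7–8 in Part C) | none stated | 4 (2 unbound) | 0 | 2 unbound |
| 9 | none stated | 2 | 2 | 2 |

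**Designated before/after pairs for heart failure.** Label followed: 0 of up to 30. Overview followed: up to 30 of 30. For COPD it is up to 30 on either reading. All are upper limits before dropout, since the overview says only that participants may be required to do all three parts.

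**Can Parts A and B supply the baseline?** Heart failure participants perform 1 + 2 + 6 = 9 challenges there, but:
- The overview assigns Visits 1–3 to question one and Visits 4–6 to question two. Only Visits 7–9 serve question four and aim vii.
- Settings differ between Parts A and B, and Part C states neither speed nor gradient, so comparability with Visit 9 cannot be established.
- One of the two challenges at Visits 2–3 uses the gas-exchange mask, which the protocol itself treats as affecting dyspnea ratings.
- Their timing relative to rehabilitation is not stated.

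Using them as the baseline would therefore be an assumption that the protocol does not make.

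**Texts side by side.** For heart failure attending before rehabilitation: aim iv, the overview, the timing phrase in the Part C sentence, the clause limiting only binder wearing to COPD, and the unrestricted Visit 9. Against: the label on Visits 7 and 8, and a test list written around the binder.

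**The case against.** The strongest reply is that the heart failure baseline is already in the protocol. The overview names heart failure and plans two challenges before and after. It describes those in the acute part as a separate group. In Part C only binder wearing is limited to COPD, a limit that would be redundant if no one else attended. Part C also cites Figure 1 for the split between the acute and chronic interventions, and the figure may show who attends which visit.

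This stands as far as intent goes. A reader might infer that heart failure participants have no baseline challenge at all, or that their part of aim iv cannot be computed. The documents do not support either as an unconditional statement: nine earlier challenges exist, and the overview provides for the missing two. What the reply does not remove is the label itself, which sits in the visit-by-visit schedule that sites would work from, or the lack of any heart failure test list there.

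A reader might also infer that COPD participants barred from the binder lose their rehabilitation baseline. That is not established. The exclusion item does not say whether it removes someone from the binder tests or from all of Part C.

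Nor does a comparison of precision with and without heart failure help. The protocol gives no standard deviation and plans no pooling of the two diseases.

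**Conclusion.** The point holds as an internal contradiction that bears on a primary aim. The label on Visits 7 and 8 conflicts with the rest of its own sentence, the Study Procedure overview, Visit 9 and aim iv.

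The size is conditional. If the label governs, heart failure yields no designated before/after pair, its part of aim iv could not be estimated as designed, and the minimally important difference in aim vii gets no heart failure rehabilitation change. Aim vii promises a value for the challenge, not one per disease, so it would be narrowed and not lost. If the overview governs, the comparison is intact.

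This rests on the text alone, with Figure 1 unseen. It is also separate from the eligibility item requiring a completed rehabilitation programme: correcting that would still leave the heart failure pre-rehabilitation visit undefined. Because a missed baseline is irrecoverable, the correction should be made before any heart failure participant in Part C starts rehabilitation.

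**What to change.** 1. In Part C, attach the COPD-only restriction to the binder tests and remove it from the pre-rehabilitation visit.
2. Schedule for heart failure participants the two pre-rehabilitation challenges without a binder that the overview already plans, and state at which visit or visits they take place.
3. State that these challenges are the baseline for the rehabilitation comparison and are run under the same conditions as Visit 9. Part C should state those conditions, including speed and gradient, which it now omits.
4. Bring the overview, Part C and Figure 1 into agreement.
5. Reconcile the Exclusion Criteria with Part C on whether the binder-related item removes a participant from the binder tests only or from all of Part C. That is for the investigators to decide; this review proposes no rule.

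The cost is a protocol wording and visit-schedule amendment. It adds no new procedure, since the overview already provides for these two challenges.
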